8.1. Primary objectives

The primary objectives in this study are to describe:

- Clinical characteristics and demographics of patients using anticoagulation therapy for the treatment of VTE (rivaroxaban oral suspension or SOC)
- Use of anticoagulation therapy (including selected drug, dose, and duration) for treatment of VTE
- Incidence and severity of bleeding (major bleeding, and CRNM bleeding) according to anticoagulation therapy (rivaroxaban oral suspension or SOC)

8.2. Secondary objectives

The secondary objectives in this study are to describe:

- Time trends in patient characteristics and anticoagulation treatment patterns at the population-level over the study period
- Incidence of recurrent symptomatic VTE according to anticoagulation therapy (rivaroxaban oral suspension or SOC)
- Specialty and care setting of physicians who prescribe anticoagulation therapy (rivaroxaban oral suspension or SOC)

9. Research methods

9.1. Study design

This will be an observational, retrospective, descriptive, multi-national cohort study of children initiating anticoagulation therapy. The study will be conducted using secondary data derived from multiple data sources including electronic health records and administrative health insurance claims data in four European countries (France, Sweden, Denmark, Spain).

The study cohort will include all children aged under two years and initiating anticoagulant therapy following a VTE diagnosis. The inclusion period will be from the market launch date of rivaroxaban oral suspension in each country until end of 2026, with follow-up until end of 2027. Patients will be followed up from the anticoagulation therapy initiation (index date), until occurrence of bleeding (major bleeding, and CRNM bleeding as co-primary outcomes) or recurrent symptomatic VTE (as secondary outcome) – with time at risk specific to each outcome, discontinuation of all study drugs, death, exit or last available data from the data source, or end of study period, whichever occurs first. Two exposure categories will be defined, one for rivaroxaban and one for SOC, using an as-treated exposure definition. Patients will contribute time to both exposure categories if they switch from SOC to rivaroxaban or vice versa. As long as the anticoagulant treatment period is continuing, patients will be allowed to switch multiple times between SOC and rivaroxaban and contribute time accordingly to both exposure categories.

[figure not shown]
If patients have another initiation of anticoagulant therapy for a VTE diagnosis before the age of two years, and for which they fulfil all inclusion and exclusion criteria (including a 6-month washout period), they will be allowed to enter the study cohort again with a new index date.

22195; XAPAEDUS; v 2.1, 16 NOV 2022;

Page 17 of 59

based on template version 9

An overview of the study design is presented in [Figure 1](#).

DOAC = direct oral anticoagulant; SOC = standard of care; VKA = vitamin K antagonist; VTE = venous thromboembolism

- ^a. Patients will be followed in two exposure categories, rivaroxaban or SOC (heparins, VKAs, other DOACs). Treatment episode of rivaroxaban oral suspension OR SOC defined by cumulative days of supply from consecutive dispensations, until discontinuation (grace period of 30 days allowed and 30-day carry-over period) or switch to other anticoagulation therapy. During an anticoagulation treatment period, switches from SOC to rivaroxaban and vice versa are allowed.
- ^b. Baseline conditions: demographics, characteristics of the index VTE, co-morbidities, prior treatment.
- ^c. Censoring criteria will be the earliest of: discontinuation of all study drugs (rivaroxaban and SOC), death, disenrollment/de-registering/emigration, last available data, end of the study period.

Adapted from Schneeweiss S et al. Graphical Depiction of Longitudinal Study Designs in Health Care Databases. *Ann Intern Med.* 2019 Mar 19;170(6):398-406.

Figure 1 Study design diagram

The strengths of this study design to answer the research question include:

- Use of population-based secondary health data sources which capture observational data from routine clinical practice. This avoids the possibility to influence prescribing behaviour and reduces the risk of selection bias or recall bias due to the secondary nature of the data. The results will reflect prescribing behaviour and risk of outcomes in real-world clinical practice.
- Selection of secondary health data sources providing large population coverage and/or population size, as well as broad coverage of health care settings from different geographical locations and health care systems. This will help: i) maximizing study size in this rare clinical condition, ii) providing ability to identify and follow-up the study population by capturing relevant diagnoses, drugs, and outcomes, and iii) ensuring representativeness for the general target population.
- Use of a new user design, where the at-risk period begins on the date of first observed record of anticoagulation therapy (index date), instead of the preceding VTE date.
- Contextualization of the use of and outcomes with rivaroxaban oral suspension by available contemporary treatment options.

9.2. Setting

9.2.1. Study population

The source population will consist of children aged under two years who initiate an anticoagulation therapy with rivaroxaban oral suspension or any other anticoagulation drug following a VTE diagnosis. The study population will be drawn from population-based data sources in four countries and include all patients who fulfil all inclusion and exclusion criteria during the study period.

9.2.2. Study time frame

9.2.2.1. Index date and follow-up

The index date will be the day of initiation of any anticoagulation therapy (rivaroxaban oral suspension or SOC). Patients will be assigned to two exposure categories, rivaroxaban or SOC, according to their actual use of the respective anticoagulation therapy. They may contribute time at risk to more than one exposure category if they switch from one to the other. More specifically, patients will be allowed to switch multiple times between SOC and rivaroxaban and contribute time accordingly to both exposure categories, as long as the same anticoagulant treatment period is continuing.

Patients will be followed from the index date to the earliest of the following censoring criteria:

- End of the anticoagulation treatment period, i.e., discontinuation of all study drugs (rivaroxaban and SOC),
- Death,
- Disenrollment/de-registering/emigration or last available data,

- End of the study period.

Moreover, patients will be followed until the first occurrence of each safety/effectiveness outcome event, with time at risk defined separately for each outcome analysis.

If patients have another initiation of anticoagulant therapy (SOC or rivaroxaban) for a VTE diagnosis before the age of two years, i.e., another qualifying anticoagulant treatment period for a recurrent VTE observed during the inclusion period for which they fulfil all inclusion and exclusion criteria (including a 6-month washout period), they will be allowed to enter the study cohort again, with a new index date.

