9.2.3. Selection criteria

9.2.3.1. Inclusion criteria

Participants are eligible to be included in the study only if all of the following criteria apply:

- Evidence of initiation of an anticoagulant therapy (index drug), either rivaroxaban oral suspension or other anticoagulation therapies (heparins, VKAs, other DOACs). Initiation will be defined as a first record of any anticoagulation therapy (rivaroxaban or SOC) without any anticoagulation therapy in the previous 6 months, or since date of birth for children less than 6 months (see codes for anticoagulant drugs in [Annex 3](#)).
- Evidence of a prior VTE diagnosis (index VTE), defined as the presence of at least one primary/main or secondary diagnosis code for VTE recorded in inpatient setting in the previous 30 days (see preliminary list for VTE codes in [Annex 3](#)).
- Age less than two years on index date.
- Baseline period for availability of patient data history in the data source. A minimal baseline period of six months before index date for children aged between six months and two years, and a baseline period since birth for children less than six months of age will be required.

According to its indication, rivaroxaban oral suspension should be used after at least five days of initial parenteral anticoagulation treatment. In order to describe the actual clinical practice in real world settings, there will no requirement on this initial parenteral anticoagulation treatment to include patients in the study population, so patients will be identified independently of this. In theory, all patients receiving rivaroxaban should be switchers. In practice, they may appear as initiating directly with rivaroxaban: the observed initial anticoagulant therapy might be different from the actually received initial therapy, if patients have switched drug during hospital stay and if inpatient drug data is not captured. Depending on availability of inpatient drug data in each data source, the observed initiation of the anticoagulant therapy will be identified either in outpatient or in inpatient setting, as shown in [Figure 2](#) below (see [Section 9.4](#)).

SOC for treatment of VTE in children usually include UFH, LMWH and VKA and may vary across countries. With other DOACs receiving indication for VTE in paediatrics, SOC may also evolve over time.

Figure 2 Visualization of patient journey

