 - For all agents, a grace period of 30 days will be used. Thus, a treatment episode will be considered discontinued if a gap >30-day grace period is observed between consecutive prescriptions of the same agent. A 30-day period will be added at the end of the treatment episode of each agent to account for a carry-over effect unless a drug switch is observed.
- **Drug switch:** defined whenever a prescription of another anticoagulant agent is recorded during a treatment episode of the prior anticoagulant agent.
- Treatment episodes for the individual SOC agents that are overlapping or separated by less than the 30-day grace period will be collapsed into a single SOC treatment episode.

- **Anticoagulant treatment period:** defined as a sequence of treatment episodes of rivaroxaban and SOC, i.e., from the initial treatment episode of the first agent at index date and all potential consecutive switch(es) to other agents. An anticoagulation treatment period will be considered discontinued when all study drugs of interest are discontinued.

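### An anticoagulant restarted after the discontinuation gap but before 6 drug-free months is counted nowhere: it neither resumes follow-up nor allows re-entry

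*Protocol*

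**What the plan says.** All references are to the protocol.

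- **Censoring (9.2.2.1).** Follow-up stops at the earliest of several events, one of which is "End of the anticoagulation treatment period, i.e., discontinuation of all study drugs (rivaroxaban and SOC".
- **When a drug counts as stopped (9.3.1).** "a treatment episode will be considered discontinued if a gap >30-day grace period is observed between consecutive prescriptions of the same agent". In addition, "A 30-day period will be added at the end of the treatment episode of each agent to account for a carry-over effect", unless a switch is seen. For the whole sequence of agents, "An anticoagulation treatment period will be considered discontinued when all study drugs of interest are discontinued".
- **Time in the other category (9.2.2.1).** Children who change drug "contribute time accordingly to both exposure categories, as long as the same anticoagulant treatment period is continuing". A switch is "defined whenever a prescription of another anticoagulant agent is recorded during a treatment episode of the prior anticoagulant agent" (9.3.1).
- **Coming back (9.1, 9.2.2.1, 9.2.3.1).** Re-entry with a new index date requires "another qualifying anticoagulant treatment period for a recurrent VTE observed during the inclusion period", with every inclusion criterion met again. One of these is a first anticoagulant record "without any anticoagulation therapy in the previous 6 months, or since date of birth for children less than 6 months". The others include an inpatient VTE code in the prior 30 days and age under two.

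No section provides for resuming follow-up under the original index date. The limitations in 9.9 do not mention children who restart early.

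**The concern.** The 30-day rule closes a treatment period, and the 6-month rule decides whether a new one may open. Nothing covers the months between them. For example, a child has a heparin course, stops, and starts rivaroxaban 10 weeks later. The start is not a switch, because the earlier episode is over. It is not an initiation either, because the washout fails. That child does not appear as a rivaroxaban user, and a bleed on that course is not counted. With a 7-month gap, and the other criteria met, the same child would be a new entrant.

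Two primary objectives are touched: use of anticoagulants (drug, dose, duration) and bleeding by therapy. Two features of the data could also create gaps where treatment did not stop:

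- Section 9.9 says that SNDS and the Swedish registers do not capture inpatient drugs. A child readmitted for several weeks on anticoagulation and discharged on rivaroxaban can look as if treatment had lapsed. SNDS is the one source where outcome analysis is expected to be feasible (9.5.2, 9.7.8).
- For rivaroxaban suspension and VKAs, episode length is inferred from the distribution of refill intervals (9.3.1), so some apparent gaps over 30 days will be measurement error.

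**Working it through.** **1. The protocol's own counts.** These serve only as a scale, since the point concerns a follow-up rule.
- Mean of the yearly market shares (9.5.2): (10 + 32 + 38 + 42 + 50 + 30)/6 = 33.67%.
- Rivaroxaban children, SNDS: 650 × 0.3367 = 218.8 (Table 6: 219). Overall: 846 × 0.3367 = 284.8 (Table 6: 285).
- SNDS rivaroxaban bleeds, major plus CRNM: 218.8 × 5.6% = 12.25 (Table 6: 12).

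The figures reproduce.

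**2. The uncovered interval.** Let g be the days from end of supply to restart, with 6 months taken as 183 days.

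| g | 30-day grace only | carry-over stacked on grace |
|---|---|---|
| 1–30 | period continues | period continues |
| 31–60 | uncovered | period continues |
| 61–182 | uncovered | uncovered |
| 183 or more | re-entry, if a new inpatient VTE code and age under two | same |

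Length: 182 − 31 + 1 = 152 days, or 182 − 61 + 1 = 122 days. The 10-week example (day 70) is uncovered on both readings.

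Three things are not settled by the text:
- Whether carry-over runs inside or after the grace period.
- Whether a different agent started during carry-over counts as a switch.
- Whether the washout runs from the last record or from end of supply. If from the last record, the upper bound falls by one supply length; with an assumed 30-day supply it becomes day 182 − 30 = 152.

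For a child under 6 months the washout runs since birth, so a previously treated child cannot re-enter before 6 months of age.

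**3. Possible size, under assumptions.** The protocol gives no restart frequency. Assume that restarts follow recurrences, that 25–75% of recurrences lead to a restart in the interval, and that the mean market share applies to restarts. Then children affected = N × recurrence × share in interval.

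| Recurrence input | Of 846 | Of 650 (SNDS) | SNDS on rivaroxaban (× 0.3367) | SNDS rivaroxaban bleeds (× 5.6%) |
|---|---|---|---|---|
| 7–20% (7.2) | 14.8–126.9 | 11.4–97.5 | 3.8–32.8 | 0.2–1.8 |
| 1.2–3.0% (trial, 7.2) | 2.5–19.0 | 1.9–14.6 | 0.7–4.9 | 0.04–0.28 |

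The French suppression rule applies to counts below ten (9.7.8). Going from 12 to 9 would take a loss of 3, which is outside both ranges. Apparent restarts caused by unseen inpatient treatment or by estimated supply are not in this table, and the protocol gives nothing from which to size them.

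**The case against.** The strongest reply is that this is a deliberate design. New-user entry, as-treated exposure and a 6-month washout are ordinary choices, they do not contradict each other, and keeping out re-treatment of recently treated patients is what a washout is for. That stands, and it is why the main analysis should not change. It does not explain why a drug-utilization study should leave these courses uncounted and the interval unmentioned.

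A reader might infer more than the protocol supports:

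- **That the washout loses the recurrences that prompt a restart.** It does not. Recurrence after stopping is outside as-treated time at risk (9.7.4), whatever the washout. In a child who re-enters after 7 months, that recurrence is an index VTE, not an outcome.
- **That the loss falls mainly on rivaroxaban.** The SOC-then-rivaroxaban sequence in 9.2.3.1 and 9.9 describes a switch within one treatment period, which is captured. At the protocol's mean share, about two-thirds of restarts (100 − 33.67 = 66.33%) would be SOC, and some children restarting rivaroxaban are already counted as users.
- **That the loss is large.** The 7–20% recurrence in 7.2 has no time horizon and covers all paediatric ages. The same section calls recurrence uncommon once the cause is resolved and places all four rivaroxaban-arm recurrences in the trial at age 12 to under 18. Setting an assumed number of restarts on any drug against 285 rivaroxaban children would also mix two different units.

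Resuming follow-up in the main analysis would have a cost as well: it would admit treatment without a recent VTE code and put interrupted time into the Kaplan-Meier estimates.

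**Conclusion.** The mechanism holds as the rules are written. Restarts from day 31 (or day 61) to about day 182 after end of supply are not represented, and no other section recovers them. What is lost is the later course: its drug use, its time at risk and any bleed on it. The first course is kept.

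The number affected cannot be derived from the protocol and may be small. The scenarios give about 2.5 to 127 of 846 children and fewer than 2 SNDS rivaroxaban bleeds, resting on an assumed 25–75% share and on recurrence figures from other settings. Neither a directional bias against rivaroxaban nor a threat to the main bleeding result is shown. This is a low-cost improvement to the completeness of two primary objectives, not the correction of an invalid analysis.

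**What to change.** Keep the 6-month washout, the re-entry rule and the main as-treated new-user analysis unchanged, and add the following.

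1. **Sections 9.3.1 and 9.7.3.** Define a restart as any study drug recorded after discontinuation of the treatment period but within 6 months of it, at age under two. Flag and count restarts by agent. Report whether an inpatient VTE code was recorded in the prior 30 days and whether a hospital stay spans the gap. Show first rivaroxaban use at restart as a separate row in the drug-use description.
2. **Section 9.7.6.1.** Add a sensitivity analysis of crude incidence rates that adds restart time at risk to the category of the restarted drug, with drug-free days excluded.

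The definition needs the day on which discontinuation takes effect, so 9.3.1 should also state whether carry-over runs inside or after the grace period.

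The cost is protocol wording and a little programming. Applying the re-entry rule already means examining anticoagulant records and inpatient codes after the first period ends. Some restarts may be prophylaxis rather than VTE treatment, hence the flag and the separate display. Where counts fall under a source's disclosure threshold, stating that they do is still informative.

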9.2.2.2. Study period

At this stage it is assumed that the study will last at least seven years to provide enough time to ensure the achievement of the sample size (see [Section 9.5](#)). The inclusion period will start on the market launch date of rivaroxaban granules for oral suspension 1 mg/mL in the respective countries. The countries were selected based on the potential data sources that were investigated during the feasibility phase (see [Section 9.4.1](#)). A description of market authorization status in the different potential countries along with launch date is provided in [Table 2](#).

The study period would end 31 DEC 2027, with the inclusion period ending 31 DEC 2026 to allow a minimum potential follow-up of 12 months.

Table 2: Market presence of rivaroxaban granules for oral suspension 1 mg/mL (as of August 2022)

Country	Marketing authorization status	Marketing authorization date	Reimbursement status	Reimbursement date	Market entry date	Distribution channel ^a	Availability of rivaroxaban oral suspension after market penetration ^b
Denmark	Granted	February 2021	Y	17/05/2021	October 21	Hospital and Retail	High
Finland	Granted	February 2021	Y	08/05/2021	September 2021	Hospital and Retail	High
Sweden	Granted	February 2021	Y	22/10/2021	September 2021	Hospital and Retail	High
France	Granted	February 2021	Y	18/04/2022	April 2022	Hospital and Retail	High
Germany	Granted	February 2021	Y	21/01/2021	May 21	Hospital and Retail	High
Italy	Granted	February 2021	N	Expected September 2022	Pending	Pending	Moderate
Netherlands	Granted	February 2021	Y	07/01/2021	July 2021	Hospital and Retail	High
Spain	Granted	February 2021	N	Pending	Pending	Hospital and Retail	Moderate
UK	Granted	February 2021	Y	21/01/2021	April 2021	Hospital and Retail	High
Canada	Granted	January 2021	N	Pending	May 2021	Pending	High

^a Retail pharmacy, hospital pharmacy, other institutional care

^b High (marketing authorization and reimbursement obtained, and has entered market), moderate (marketing authorization obtained, but reimbursement and/or market entry pending), poor (marketing authorization, reimbursement and market entry pending)

9.2.3. Selection criteria

9.2.3.1. Inclusion criteria

Participants are eligible to be included in the study only if all of the following criteria apply:

- Evidence of initiation of an anticoagulant therapy (index drug), either rivaroxaban oral suspension or other anticoagulation therapies (heparins, VKAs, other DOACs). Initiation will be defined as a first record of any anticoagulation therapy (rivaroxaban or SOC) without any anticoagulation therapy in the previous 6 months, or since date of birth for children less than 6 months (see codes for anticoagulant drugs in [Annex 3](#)).
- Evidence of a prior VTE diagnosis (index VTE), defined as the presence of at least one primary/main or secondary diagnosis code for VTE recorded in inpatient setting in the previous 30 days (see preliminary list for VTE codes in [Annex 3](#)).
- Age less than two years on index date.
- Baseline period for availability of patient data history in the data source. A minimal baseline period of six months before index date for children aged between six months and two years, and a baseline period since birth for children less than six months of age will be required.

According to its indication, rivaroxaban oral suspension should be used after at least five days of initial parenteral anticoagulation treatment. In order to describe the actual clinical practice in real world settings, there will no requirement on this initial parenteral anticoagulation treatment to include patients in the study population, so patients will be identified independently of this. In theory, all patients receiving rivaroxaban should be switchers. In practice, they may appear as initiating directly with rivaroxaban: the observed initial anticoagulant therapy might be different from the actually received initial therapy, if patients have switched drug during hospital stay and if inpatient drug data is not captured. Depending on availability of inpatient drug data in each data source, the observed initiation of the anticoagulant therapy will be identified either in outpatient or in inpatient setting, as shown in [Figure 2](#) below (see [Section 9.4](#)).

SOC for treatment of VTE in children usually include UFH, LMWH and VKA and may vary across countries. With other DOACs receiving indication for VTE in paediatrics, SOC may also evolve over time.

Figure 2 Visualization of patient journey

